6.4 Changes in HbA1c, etc. by Factor Probably Affecting Efficacy

(1) Patients to be tabulated and analyzed

Efficacy Analysis Set

(2) Details of tabulation and analysis

For changes in HbA1c (NGSP values), summary statistics and the mean 95% confidence intervals will be calculated and the paired t-test will be performed at each testing time point (start of Nesina treatment, 3 months, 6 months, 12 months, 24 months, and 36 months after Nesina treatment and last evaluation).

The Glycemic control achievement rate for HbA1c ($< 7.0\%$, $\geq 7.0\%$ / $< 6.0\%$, $\geq 6.0\%$) at each testing time point (start of Nesina treatment, 3 months, 6 months, 12 months, 24 months, and 36 months after Nesina treatment and last evaluation) will be tabulated at the following parameters:

i Sex (Male, Female)

ii Age (< 65 years, ≥ 65 years)

iii Age (< 75 years, ≥ 75 years)

iv Concurrent renal disorder (No, Yes)

v HbA1c (NGSP value) at the start of Nesina treatment ($< 6.0\%$, 6.0% to $< 7.0\%$, 7.0% to $< 8.0\%$, $\geq 8.0\%$)

vi Mean daily dose of Nesina (> 25 mg, 25 to > 12.5 mg, 12.5 to > 6.25 mg, or 6.25 mg)

vii Concomitant diabetic drugs (α -glucosidase inhibitors, thiazolidines, sulfonylureas, biguanides, rapid-acting insulin secretagogues, or insulin preparations)

(3) Number of tables and figures

Tables 6.4-1 to 6.4-14

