#### 10.5.2 Factors Probably Affecting Efficacy

For the changes in HbA1c and the achieving percent in glycemic control for HbA1c at 36 months after the start of treatment, the following will be stratified: patients demographics

(e.g., age, sex, HbA1c at the start of Nesina treatment) and details of treatment (e.g., status of Nesina treatment, status of concomitant medications).

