Concomitant medication (other)	Drugs other than the above (diabetic drugs, hypertension drugs, or dyslipidaemia drugs).
Protease Inhibitor	Use the results of the drug name in the survey sheet (electronic) coded with the NHI Drug List (Appendix 1. List of Protease Inhibitors).
Renal excretory drugs	Use the results of the drug name in the survey sheet (electronic) coded with the NHI Drug List (Appendix 2. List of Renal Excretory Drugs).
Nesina treatment period (days)	Actual treatment period from the start date to the end date of Nesina treatment. However, the washout period is excluded from the treatment period. Calculate using the following formula: End of Nesina treatment – start date of Nesina treatment + 1 (grand total). (Consider the washout period.)
Mean daily dose of Nesina	Calculate using the following formula: Total of “daily dose of Nesina × Nesina treatment period at the relevant dose” / Nesina treatment period. For the calculation of Nesina treatment period, refer to the above. If the daily dose of Nesina is a number outside specification in the survey sheet (electronic) and is actual number, use the relevant number.

Term	Definition
HbA1c (NGSP value)	
The NGSP value only will be used in this analysis.
 
For the HbA1c (JDS value), calculate using the following formula: $\text{NGSP value (\%)} = 1.02 \times \text{JDS value (\%)} + 0.25\%$ 
 
The HbA1c (international standard value) will be handled as the NGSP value.

Change in HbA1c	
For HbA1c converted to the NGSP value, calculate using the following formula: Laboratory value – Laboratory value at the start of Nesina treatment.

Glycemic control achievement rate	
Divide the following two categories for the Glycemic control achievement rate:
 
HbA1c (NGSP converted value) [Unit %] NGSP (%): < 6.0, ≥6.0 / < 7.0, ≥ 7.0

non-HDL cholesterol	
Calculate using the following formula: “Total cholesterol” – “HDL cholesterol.”

Summary statistics	
Number of patients, mean, standard deviation, minimum, first quartile, median, third quartile, and maximum.

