1.4 Level of Significance and Confidence Coefficient

Two-sided 5%, two-sided 95%.

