5.4 Patient Demographics and Frequency of Adverse Drug Reactions / Infections by Treatment

5.4.1 Patients demographics and Frequency of Adverse Drug Reactions / Infections by Treatment

(1) Patients to be tabulated and analyzed

Safety Analysis Set

(2) Details of tabulation and analysis

Each parameter will be categorized by the categories described below to tabulate the percent of patients with adverse drug reactions, etc.

The Fischer exact test will be used for parameters without rank data. The Mann-Whitney U test will be used for parameters with rank data. (The tests will be used for parameters with asterisk [*].)

Total and mild type 2 diabetes mellitus patients will be tabulated.

Parameter	Category
Sex*	Male, Female
Age*	< 65 years, ≥65 years
	< 75 years, ≥75 years
Severity of renal impairment*	Normal + Mild, Moderate + Severe
Concurrent liver disorder*	No, Yes
Concurrent renal disorder*	No, Yes
Concurrent heart disease*	No, Yes
Details of concurrent heart disease	Cardiac failure, myocardial infarction, or angina pectoris

Parameter	Category
(overlapped)	
Concurrent cardiac failure*	No, Yes
Severity classification of cardiac failure (NYHA classification)*	Classes NYHA I, NYHA II, NYHA III, and NYHA IV
Concurrent stroke-related disease*	No, Yes
Mean daily dose of Nesina	> 25 mg, 25 to >12.5 mg, 12.5 to > 6.25 mg, or ≤6.25 mg
Administration of concomitant medication (diabetic drug)	No, Yes
Concomitant medications (diabetic drugs) (overlapped)	α-glucosidase inhibitors, thiazolidines, sulfonylureas, biguanides, rapid-acting insulin secretagogues, or insulin preparations
Administration of concomitant medication (protease drug)*	No, Yes
Administration of concomitant medication (combined with renal excretory drug)*	No, Yes

(3) Number of tables and figures

Table 5.4.1-1

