6.5 Changes in HbA1c, etc. in Patients with Special Demographics

(1) Patients to be tabulated and analyzed

Efficacy Analysis Set.

However, patients will be evaluated for Parameter (ii) in (2) Details of tabulation and analysis.

Patients with moderate or higher renal impairment in the Efficacy Analysis Set.

(2) Details of tabulation and analysis

For changes in HbA1c (NGSP values), summary statistics and the mean 95% confidence intervals will be calculated and the paired t-test will be performed at each testing time point (start of Nesina treatment, 3 months, 6 months, 12 months, 24 months, and 36 months after

Nesina treatment and last evaluation).

The Glycemic control achievement rate for HbA1c ($< 7.0\%$, $\geq 7.0\%$ / $< 6.0\%$, $\geq 6.0\%$) at each testing time point (start of Nesina treatment, 3 months, 6 months, 12 months, 24 months, and 36 months after Nesina treatment and last evaluation) will be tabulated at the following parameters:

- i. Severity of renal impairment (Normal + Mild, Moderate + Severe)
- ii. Mean daily dose of Nesina (> 25 mg, 25 to > 12.5 mg, 12.5 to > 6.25 mg, or 6.25 mg)

(3) Number of tables and figures

Tables 6.5-1 to 6.5-4

Statistical Analysis Plan

Nesina Tablets Special Drug Use Surveillance: Mild Type 2 Diabetes Mellitus

(Final Analysis)

Takeda Pharmaceutical Company Limited.

PPD

A rectangular area of the document is redacted with a solid blue color.

PPD

A large rectangular area of the document is redacted with a solid blue color.

Version 2.0, Created on January 30, 2018

Table of Contents

1.0	Definition of Terms and Handling of Laboratory/Measured Data.....	1
1.1	Definitions	1
1.2	Important Identified Risks, Potential Risks, and Missing Information.....	10
1.3	Display digit.....	11
1.4	Level of Significance and Confidence Coefficient.....	12
1.5	Handling of Laboratory/Measured Data	12
1.6	Display Data Digit.....	12
2.0	Disposition of Patients (Patient Diagram).....	14
3.0	Patient Demographics	15
4.0	Details of Treatment.....	18
4.1	Initial Dose of Nesina and Mean Daily Dose of Nesina, by Severity of Renal Impairment.....	19
5.0	Safety Tabulation and Analysis	21
5.1	Occurrence of adverse events and adverse drug reactions / infections.....	21
5.1.1	Occurrence of adverse events.....	21
5.1.2	Occurrence of adverse drug reactions / infections.....	21
5.1.3	Important Identified Risks, Important Potential Risks, and Important Missing Information....	22

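### The efficacy factor tables (SAP 6.4 and 6.5) test each subgroup's HbA1c change against zero and give no between-subgroup estimate, so their p-values reflect subgroup size and do not compare subgroups

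*SAP*

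**What the plan says.** Protocol 10.5.2 deals with factors probably affecting efficacy. For the HbA1c change and the control rate it says "at 36 months after the start of treatment, the following will be stratified" by demographics and treatment details. Protocol 10.6 adds an evaluation of renal severity and dose.

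SAP 6.4 carries this out for seven parameters: sex, two age splits, concurrent renal disorder, start HbA1c, mean daily dose and concomitant diabetic drug class. Its only inferential step is: "For changes in HbA1c (NGSP values), summary statistics and the mean 95% confidence intervals will be calculated and the paired t-test will be performed". SAP 6.5 repeats the method for item (i), "Severity of renal impairment (Normal + Mild, Moderate + Severe", and for item (ii), mean daily dose in patients with moderate or severe impairment. SAP 1.1 defines the change as "Laboratory value – Laboratory value at the start of Nesina treatment". The level is two-sided 5% (SAP 1.4).

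Read strictly, the list of parameters in 6.4 hangs only on the control-rate sentence. The output list, "Tables 6.4-1 to 6.4-14", settles it: 14 tables are 7 parameters times 2 outcomes, so the change and its t-test are stratified too. SAP versions 1.0 and 2.0 specify the same tests.

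The safety counterpart, SAP 5.4.1, does compare levels: "The Fischer exact test will be used for parameters without rank data", with Mann-Whitney for ranked factors. This applies to the starred factors, which include sex, age, renal disorder and renal severity.

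**The concern.** A paired t-test within a level asks whether that level moved from its own start value. To learn whether a factor is related to response one must compare levels, and no between-level difference, interaction test or model is specified in 6.4 or 6.5.

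Two misreadings can follow. A small level may be non-significant next to a large significant one although both changed by the same amount. And when all levels are large, all are significant, which can look like a uniform response when the changes differ materially. Start HbA1c is recorded and is itself parameter (v), but nothing adjusts the other comparisons for it.

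At stake is how the final report answers the factor question, above all for renal severity, which has its own protocol section.

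**Working it through.** **Number of tests.** Levels in 6.4: 2+2+2+2+4+4+6 = 22. Post-start time points: 3, 6, 12, 24 and 36 months and last evaluation = 6. That gives 22 x 6 = 132 paired tests. The start HbA1c level of 8.0% or more should be empty, because SAP 2.0 removes patients without mild disease from the Efficacy Analysis Set and SAP 1.1 sets mild at NGSP 7.4% or below (the protocol's JDS limit converts to 1.02 x 7.0 + 0.25 = 7.39). So 21 x 6 = 126 remain. SAP 6.5 adds (2+4) x 6 = 36. None compares levels.

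**Subgroup sizes in the documents.** Protocol 3.2 counts 1864+226+175+273+109 = 2647 patients and scales them to 20000. The largest group is 20000 x 1864/2647 = 14084 and the smallest 20000 x 109/2647 = 824, as the protocol states. These are drug classes, used here only as plausible sizes. No size is given for the renal, age or dose levels, and no SD of HbA1c change.

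**Small levels.** Assume a true change of -0.10 in every level. Power of the within-level t-test (noncentral t, noncentrality 0.10 x sqrt(n)/SD, two-sided 5%):

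| n | SD 0.5 | SD 0.6 | SD 0.7 | SD 1.0 |
|---|---|---|---|---|
| 50 | 28% | 21% | 17% | 11% |
| 100 | 51% | 38% | 29% | 17% |
| 200 | 80% | 65% | 52% | 29% |
| 824 | >99.9% | 99.8% | 98% | 82% |

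At SD 0.6, a level of 14084 is significant practically always. Beside it, a level of 50 is non-significant in 100 - 21 = 79% of surveys and a level of 100 in 100 - 38 = 62%, with no true difference. At n=824 this falls to 0.2%. A true change of -0.20 raises power to 64% (n=50) and 91% (n=100).

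**Large levels.** Let the true changes be -0.4 (n=14084) and -0.2 (n=824), SD 0.6. The expected t statistics are 0.4 x sqrt(14084)/0.6 = 79 and 0.2 x sqrt(824)/0.6 = 9.6. Both are far beyond 1.96, so the tests report the same result for a twofold difference. A direct comparison has SE = 0.6 x sqrt(1/824 + 1/14084) = 0.0215, a CI half-width of 1.96 x 0.0215 = 0.042 and a ratio of 0.2/0.0215 = 9.3. Over SD 0.5 to 1.0 the half-width is 0.035 to 0.070.

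**Start HbA1c.** An unadjusted difference carries slope x imbalance. Neither is in the documents. If levels differed by 0.2 to 0.4 at the start and the slope were -0.2 to -0.5, the artefact would be 0.2 x 0.2 = 0.04 to 0.4 x 0.5 = 0.20 points. This only illustrates the scale.

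**The case against.** The strongest reply is that the tables hold more than p-values. SAP 1.1 defines the summary statistics as "Number of patients, mean, standard deviation, minimum, first quartile, median, third quartile, and maximum", and 6.4 adds the 95% CI of the mean change. For disjoint levels a reader can form the difference and its CI, and a small level with a mean of -0.10 and a wide interval need not be read as a non-response. This stands. A reader might infer that the tables cannot show any factor effect. That is true of the tests, not of the whole table. The comparison so obtained is still indirect and unadjusted for start HbA1c.

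Second, the protocol promises tabulation and stratification, and no between-level test. This also stands: an inference that the SAP breaches the protocol is not supported.

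Third, a reader might infer that the tables will mislead whenever subgroup sizes differ. The documents do not support that. The 62-79% figures need levels of 50 to 100 patients and a change near -0.10. At 824 the split almost vanishes at SD 0.6, and even at half that size (412) power is 92%.

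Fourth, the safety parallel is partial. Mean dose and concomitant diabetic drug carry no star in 5.4.1, so safety does not test them either. The parallel holds for 6.4(i-iv) and 6.5(i).

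Finally, modelling drug class could do harm. SAP 1.1 counts any drug taken after Nesina starts as concomitant, including one added because HbA1c was poor. A between-class estimate would then be open to reverse causation. This limits the fix.

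**Conclusion.** The point holds as a weakness of method. The only tests in SAP 6.4 and 6.5 set each level's change against zero, their p-values track level size, and no between-level estimate is planned, although the SAP makes such comparisons for adverse drug reactions on several of the same factors.

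The size depends on numbers that the documents do not give. If the renal, age or dose levels hold 50 to 100 patients and the true change is about -0.10 (SD 0.6), discordant significance without a true difference is more likely than not. With levels of 824 or more it is rare at that SD, and the problem becomes the reverse: everything is significant. In neither case do the p-values say whether a factor matters.

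**What to change.** - **6.4(i-iv) and 6.5(i):** at 36 months and last evaluation, fit an ANCOVA of HbA1c change on factor level with start HbA1c as covariate. Report the between-level difference with its two-sided 95% CI. Label it exploratory and as association only, because there is one arm and SAP 1.5 takes 36-month data from patients who continued.
- **Within-level results:** keep means and 95% CIs as description. Drop the paired-test p-values, or state in a footnote that they do not compare levels.
- **6.4(v):** report the regression of change on start HbA1c and remove the level of 8.0% or more.
- **6.4(vii):** do not apply the ANCOVA to concomitant drugs as defined. At most, use diabetic drugs already in use when Nesina started.

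The cost is revised SAP wording, a short additional program and a few more exploratory estimates to present with care. No new data are needed.

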6.5 Changes in HbA1c, etc. in Patients with Special Demographics

(1) Patients to be tabulated and analyzed

Efficacy Analysis Set.

However, patients will be evaluated for Parameter (ii) in (2) Details of tabulation and analysis.

Patients with moderate or higher renal impairment in the Efficacy Analysis Set.

(2) Details of tabulation and analysis

For changes in HbA1c (NGSP values), summary statistics and the mean 95% confidence intervals will be calculated and the paired t-test will be performed at each testing time point (start of Nesina treatment, 3 months, 6 months, 12 months, 24 months, and 36 months after

Nesina treatment and last evaluation).

The Glycemic control achievement rate for HbA1c ($< 7.0\%$, $\geq 7.0\%$ / $< 6.0\%$, $\geq 6.0\%$) at each testing time point (start of Nesina treatment, 3 months, 6 months, 12 months, 24 months, and 36 months after Nesina treatment and last evaluation) will be tabulated at the following parameters:

- i. Severity of renal impairment (Normal + Mild, Moderate + Severe)
- ii. Mean daily dose of Nesina (> 25 mg, 25 to > 12.5 mg, 12.5 to > 6.25 mg, or 6.25 mg)

(3) Number of tables and figures

Tables 6.5-1 to 6.5-4

Statistical Analysis Plan

Nesina Tablets Special Drug Use Surveillance: Mild Type 2 Diabetes Mellitus

(Final Analysis)

Takeda Pharmaceutical Company Limited.

PPD

A rectangular area of the document is redacted with a solid blue color.

PPD

A large rectangular area of the document is redacted with a solid blue color.

Version 2.0, Created on January 30, 2018

Table of Contents

1.0	Definition of Terms and Handling of Laboratory/Measured Data.....	1
1.1	Definitions	1
1.2	Important Identified Risks, Potential Risks, and Missing Information.....	10
1.3	Display digit.....	11
1.4	Level of Significance and Confidence Coefficient.....	12
1.5	Handling of Laboratory/Measured Data	12
1.6	Display Data Digit.....	12
2.0	Disposition of Patients (Patient Diagram).....	14
3.0	Patient Demographics	15
4.0	Details of Treatment.....	18
4.1	Initial Dose of Nesina and Mean Daily Dose of Nesina, by Severity of Renal Impairment.....	19
5.0	Safety Tabulation and Analysis	21
5.1	Occurrence of adverse events and adverse drug reactions / infections.....	21
5.1.1	Occurrence of adverse events.....	21
5.1.2	Occurrence of adverse drug reactions / infections.....	21
5.1.3	Important Identified Risks, Important Potential Risks, and Important Missing Information....	22

1.0 Definition of Terms and Handling of Laboratory/Measured Data

1.1 Definitions

Term	Definition
Nesina	Nesina tablet(s) is abbreviated as Nesina in this statistical analysis plan.
SOC	System Organ Class of MedDRA/J MedDRA/J version 20.1 is used for this document.
HLGT	High level group term of MedDRA/J
PT	Preferred term of MedDRA/J
LLT	Lowest level term of MedDRA/J
Registered patients	Patients whose registration was approved
Survey sheet (electronic) collected patients	Patients whose survey sheets were sent via CCI [REDACTED]
Survey sheet (electronic) uncollected patients	Of the registered patients, patients whose survey sheets (electronic) were uncollected.
Safety Analysis Set	Of the survey sheet (electronic) collected patients, patients who were evaluated for safety analysis. For tabulation, the description of “total” means the Safety Analysis Set.
Not Safety Analysis Set	Of the survey sheet (electronic) collected patients, patients who were excluded from safety analysis
Efficacy Analysis Set	Of the Safety Analysis Set, patients who were evaluated for efficacy analysis
Not Efficacy Analysis Set	Of the Safety Analysis Set, patients who were excluded from the efficacy analysis
First date of Nesina treatment	Of the start dates of the Nesina treatment period in patients, the earliest date is defined as the first date of Nesina treatment.
Last date of Nesina treatment	Of the last dates of the Nesina treatment period in patients, the latest date is defined as the last date of Nesina treatment. If Nesina treatment is continued and the year, month, and date of the continued treatment period are specified, the year, month, and date of the continued treatment period are defined as the last date of Nesina treatment. If the data for the year, month, and date of the continued treatment period are missing, the following date is defined as the last date of Nesina treatment. (1) First date of Nesina treatment + 3 years (same month and date), if Nesina treatment is continued based on the survey sheet (electronic) after 36 months of treatment* (2) For other than the above, the first date of Nesina treatment + 1 year (same month and date), if Nesina treatment is continued based on the survey sheet (electronic) after 12 months of treatment**

Term	Definition
	
For the continued treatment of Nesina, the following is considered as the “treatment to be continued:”
 
 ● [End of Nesina tablet treatment] 
 * If “No” for “Did you discontinue Nesina tablets by 12 to 36 months after the start of treatment?” ** If “No” for “Did you discontinue Nesina tablets by 12 months after the start of treatment?”
Adverse drug reactions, etc.	
Abbreviation of “adverse drug reactions / infections”
 
Of the adverse events, events for which causal relationship to Nesina was assessed as “Not related” by the Investigator.
 
In this statistical analysis plan, “adverse drug reactions / infections” is used in the headings, while “adverse drug reactions, etc.” is used in the sentences and tables.

Serious adverse events	
Adverse events assessed as “serious” by the Investigator.
 
Events described in the MedDRA coding list in the Takeda Medically Significant AE List will be handled as serious even if the Investigator assesses as “Not serious.”

Serious adverse drug reactions	
Abbreviation of “serious adverse drug reactions / infections”
 
Of the “serious adverse events,” the events for which causal relationship to Nesina was assessed as “Not related” by the Investigator

Number of patients with events	Number of patients with adverse events or adverse drug reactions, etc.
Number of events	Number of adverse events or adverse drug reactions, etc.
Percent of patients with events	
[For safety analysis calculation in the Safety Analysis Set]
 
The formula is: $\text{Number of patients with events} / \text{Number of Safety Analysis Set} \times 100$.
 
[For safety analysis calculation in the Not Safety Analysis Set]
 
The formula is: $\text{Number of patients with events} / \text{Number of Not Safety Analysis Set} \times 100$.

Percent of events	
[For safety analysis calculation in the Safety Analysis Set]
 
The formula is: $\text{Number of events} / \text{Number of the Safety Analysis Set} \times 100$.
 
[For safety calculation in the Not Safety Analysis Set]
 
The formula is: $\text{Number of events} / \text{Number of Not Safety Analysis Set} \times 100$.

Onset period	
The formula is: Onset date of adverse events (or adverse drug reactions, etc.) – start date of Nesina treatment + 1.

Term	Definition
	For unknown onset date of adverse events (or adverse drug reactions, etc.), the onset period will be calculated as 1 day. However, if the start month and date of Nesina treatment are same as the onset month and date of adverse events (or adverse drug reactions, etc.), the onset period will be calculated as the start date of Nesina treatment.
Mild type 2 diabetes mellitus	Patients who have type 2 diabetes mellitus with HbA1c (NGSP value) of \leq 7.4% at the start date of Nesina treatment
Patients with diabetic complication	Patients with any of the following complications: diabetic nephropathy, diabetic retinopathy, or diabetic neuropathy.
Patients with diabetic nephropathy	Patients with complication of PT Code 10012660 (diabetic end stage renal disease) or 10061835 (diabetic nephropathy).
Patients with diabetic retinopathy	Patients with complication of PT Code 10012688 (diabetic retinal oedema) or 10012689 (diabetic retinopathy).
Patients with diabetic neuropathy	Patients with complication of PT Code 10012645 (diabetic autonomic neuropathy), 10012676 (diabetic mononeuropathy), or 10012680 (diabetic neuropathy).
Patients with concurrent hypertension	Patients with concurrent disease of the Standardised MedDRA Query (hereinafter SMQ) Code 20000147 (hypertension (SMQ) narrow).
Patients with concurrent dyslipidemia	Patients with concurrent disease of the SMQ Code 20000026 (dyslipidaemia (SMQ) narrow).
Patients with concurrent hyperuricemia	Patients with concurrent disease of the PT code meeting the Takeda MedDRA Query 20.1 (hereinafter, TMQ 20.1) (blood uric acid increased).
Patients with concurrent liver disorder	Patients with concurrent disease of the SMQ Code 20000005 (hepatic disorders (narrow)).
Patients with concurrent hepatic steatosis	Patients with concurrent disease of the PT Code 10019708 (hepatic steatosis).
Patients with concurrent alcoholic hepatitis	Patients with concurrent disease of the PT Code 10019728 (hepatitis alcoholic).
Patients with concurrent chronic hepatitis	Patients with concurrent disease of the PT Code 10008909 (chronic hepatitis).
Patients with concurrent hepatic cirrhosis	Patients with concurrent disease of the PT Code 10019641 (hepatic cirrhosis).
Patients with concurrent renal disorder	Patients with concurrent disease of the TMQ 20.1 (renal disease).
Patients with concurrent nephrotic syndrome	Patients with concurrent disease of the PT Code 10029164 (nephrotic syndrome).
Patients with concurrent glomerulonephritis	Patients with concurrent disease of the PT Code 10018364 (glomerulonephritis) or the PT Code 10018367 (glomerulonephritis chronic).

Term	Definition
Patients with concurrent chronic renal failure	Patients with concurrent disease of the PT Code 10064848 (chronic kidney disease) or the PT Code 10038435 (renal failure).
Patients with concurrent heart disease	Patients with concurrent disease of the SOC Code 10007541 (cardiac disorders).
Patients with concurrent cardiac failure	Patients with concurrent disease of the SMQ Code 20000004 (cardiac failure (SMQ) narrow).
Patients with concurrent myocardial infarction	Patients with concurrent disease of the SMQ Code 20000047 (myocardial infarction (SMQ) narrow).
Patients with concurrent angina pectoris	Patients with concurrent disease of the SOC Code 10007541 (cardiac disorders) and the PT Code 10036759 (prinzmetal angina), PT Code 10002383 (angina pectoris), PT Code 10058144 (postinfarction angina), PT Code 10002388 (angina unstable), or LLT Code 10065566 (microvascular angina).
Patients with concurrent stroke-related disease	Patients with concurrent disease of cerebral infarction, cerebral haemorrhage, subarachnoid haemorrhage, or transient ischaemic attack, described below.
Patients with concurrent disease cerebral infarction	Patients with concurrent disease of the PT Code 10006147 (brain stem infarction), PT Code 10008118 (cerebral infarction), PT Code 10008119 (cerebral infarction foetal), PT Code 10008034 (cerebellar infarction), PT Code 10019005 (haemorrhagic cerebral infarction), PT Code 10051078 (lacunar infarction), PT Code 10056237 (migrainous infarction), PT Code 10058571 (spinal cord infarction), PT Code 10060839 (embolic cerebral infarction), PT Code 10060840 (ischaemic cerebral infarction), PT Code 10064961 (thalamic infarction), PT Code 10067347 (thrombotic cerebral infarction), or PT Code 10069020 (basal ganglia infarction).
Patients with concurrent cerebral hemorrhage	Patients with concurrent disease of the SOC Code 10029205 (nervous system disorders) and the PT Code 10006145 (brain stem haemorrhage), PT Code 10008111 (cerebral haemorrhage), PT Code 10008112 (cerebral haemorrhage neonatal), PT Code 10008030 (cerebellar haemorrhage), PT Code 10018985 (haemorrhage intracranial), PT Code 10022840 (intraventricular haemorrhage), PT Code 10022841 (intraventricular haemorrhage neonatal), PT Code 10042365 (subdural haemorrhage neonatal), PT Code 10049236 (spinal epidural haemorrhage), PT Code 10048992 (spinal cord haemorrhage), PT Code 10050157 (cerebral haemorrhage foetal), PT Code 10052593 (meningorrhagia), PT Code 10058939 (thalamus haemorrhage), PT Code 10058940 (putamen haemorrhage), PT Code 10067057 (basal ganglia haemorrhage), PT Code 10067277 (cerebral microhaemorrhage), PT Code 10071205 (brain stem microhaemorrhage), PT Code 10071206 (cerebellar microhaemorrhage), PT Code 10072043 (central nervous system haemorrhage), or PT Code 10073563 (Spinal subdural haemorrhage).

Term	Definition
Patients with concurrent subarachnoid hemorrhage	Patients with concurrent disease of the SOC Code 10029205 (nervous system disorders) and the PT Code 10042316 (subarachnoid haemorrhage), PT Code 10042317 (subarachnoid haemorrhage neonatal), PT Code 10073564 (spinal subarachnoid haemorrhage), LLT Code 10072201 (Asymptomatic subarachnoid haemorrhage).
Patients with concurrent transient ischemic attack	Patients with concurrent disease of the SOC Code 10029205 (nervous system disorders) and the PT Code 10044390 (transient ischaemic attack).
Patients with concurrent allergic disease	Patients with concurrent disease of bronchial asthma, pollinosis, allergic rhinitis, or allergic dermatitis, described below.
Patients with concurrent bronchial asthma	Patients with concurrent disease of the SOC Code 10038738 (respiratory, thoracic and mediastinal disorders) and the PT Code 10003553 (asthma), PT Code 10075084 (aspirin-exacerbated respiratory disease), PT Code 10003557 (asthma exercise induced), PT Code 10003559 (asthma late onset), PT Code 10041961 (status asthmaticus), PT Code 10001890 (alveolitis allergic), PT Code 10049585 (infantile asthma), PT Code 10070836 (occupational asthma), or PT Code 10064823 (asthmatic crisis).
Patients with concurrent pollinosis	Patients with concurrent disease of the PT Code 10048908 (seasonal allergy).
Patients with concurrent allergic rhinitis	Patients with concurrent disease of the PT Code 10039085 (rhinitis allergic).
Patients with concurrent allergic dermatitis	Patients with concurrent disease of the PT Code 10012434 (dermatitis allergic).
Patients with concurrent malignant tumor	Patients with concurrent disease of the SOC Code 10029104 (neoplasms benign, malignant and unspecified (incl cysts and polyps)).
Patients with concurrent malignant tumor (narrow sense)	Patients with concurrent disease of the SMQ Code 20000194 (malignant tumour (SMQ) narrow).
Patients with other concurrent disease	Patients with concurrent disease other than the above (diabetic complication, hypertension, dyslipidaemia, hyperuricaemia, liver disease, renal disease, heart disease, stroke-related disease, allergic disease, malignant tumor, or malignant tumor (narrow sense)).
Severity of renal impairment	Severity of renal impairment in the patient demographic section

Term	Definition
Age	If the start month and date of Nesina treatment is earlier than the birth month and date, calculate using the following formula: Start year of Nesina treatment – birth year – 1. If the birth month and date is earlier than or equal to the start month and date of Nesina treatment, calculate using the following formula: Start year of Nesina treatment – birth year. For unknown birth date, the birth date will be calculated as the 1st day of the birth month.
BMI	Calculate using the following formula: Weight (kg) / (0.0001 × Height (cm) × Height (cm)). Indicate to one decimal place rounded from two decimals.
Disease duration of type 2 diabetes mellitus (year)	Calculate using the following formula: (start date of Nesina treatment – diagnosis period of type 2 diabetes mellitus + 1) / 365.25. For unknown diagnosis month, calculate as January. Indicate to one decimal place rounded from two decimals.
Prior medication	Medications that patients were taking within 3 months before initiation of Nesina therapy.
Concomitant medication	Medications that patients were taking after the start date of Nesina treatment.
Start date of other diabetic drug and concomitant medication (other than diabetic drug)	Calculate as the start date of survey sheet (electronic).
End date of other diabetic drug and concomitant medication (other than diabetic drug)	Calculate as the end date of survey sheet (electronic).
Diabetic drugs	Drugs of the National Health Insurance (NHI) Drug List Code starting with 3969, 3961, 3962, 2492, 2499410, 2499411, 2499415, or 2499416.
α-glucosidase inhibitors	Drugs of the NHI Drug List Code starting with 3969003, 3969004, 3969009, or 3969102.
Thiazolidines	Drugs of the NHI Drug List Code starting with 3969005, 3969007, 3969100, 3969101, or 3969103.
Sulfonylureas	Drugs of the NHI Drug List Code starting with 3961 or 3969101.
Biguanides	Drugs of the NHI Drug List Code starting with 3962, 3969100, 3969104, or 3969105.
Rapid-acting insulin secretagogues	Drugs of the NHI Drug List Code starting with 3969006, 3969008, 3969013, or 3969102.
Insulin preparations	Drugs of the NHI Drug List Code starting with 2492.
DPP-4 inhibitors	Drugs of the NHI Drug List Code starting with 3969010, 3969011, 3969012, 3969014, 3969015, 3969016, 3969017, 3969024, 3969025, 3969103, 3969104, or 3969105.

Term	Definition
GLP-1 receptor agonists	Drugs of the NHI Drug List Code starting with 2499410, 2499411, 2499415, or 2499416.
SGLT2 inhibitors	Drugs of the NHI Drug List Code starting with 3969018, 3969019, 3969020, 3969021, 3969022, or 3969023.
Combination of diabetic drugs	Drugs of the NHI Drug List Code starting with 3969100, 3969101, 3969102, 3969103, 3969104, or 3969105.
Other diabetic drugs	Other diabetic drugs not classified into the above diabetic drug categories (α -glucosidase inhibitors, thiazolidines, sulfonylureas, biguanides, rapid-acting insulin secretagogues, insulin preparations, DPP-4 inhibitors, GLP-1 receptor agonists, SGLT2 inhibitors, or combination of diabetic drugs).
Hypertension drugs	
ARB Drugs of the NHI Drug List Code starting with the following 7 numbers: 2149039, 2149040, 2149041, 2149042, 2149044, 2149046, 2149048, 2149100, 2149110, 2149111, 2149112, 2149113, 2149114, 2149115, 2149116, 2149117, 2149118, 2149119, 2149120, 2149121, 2149122
 
Ca antagonists Drugs of the NHI Drug List Code starting with the following numbers: 2149019, 2149022, 2149027, 2149030, 2149034, 2149035, 2149037, 2149038, 2149043, 2149400, 2171006, 2171014, 2171019, 2171020, 2171021, 2171022, 2171405, 2190001, 2149114, 2149115, 2149116, 2149117, 2149118, 2149120, 2149121, 2149122, 2190101, 2190102, 2190103, 2190104
 
ACE inhibitors Drugs of the NHI Drug List Code starting with the following 4 numbers: 2144
 
Diuretics Drugs of the NHI Drug List Code starting with numbers 213 or the following 7 numbers: 2149003, 2149007, 2149012, 2149110, 2149111, 2149112, 2149113, 2149119, 2149122
 
α blockers Drugs of the NHI Drug List Code starting with the following numbers: 1234400, 214200210, 2149002, 2149015, 2149023, 2149026, 1152, 1149107, 1149114, 1149115, 2531001, 2149020
 
$\alpha\beta/\beta$ blockers Drugs of the NHI Drug List Code starting with the following numbers: 2149032, 2149018, 2123014, 2149009, 2123013, 2123003, 2149008, 2149016, 2442001, 2123011, 2149036, 2123016, 2149700, 2149031, 2149010, 2123001, 2123F01, 2149029, 2123008, 2149014, 2149021,

Term	Definition
	2149028, 2123015, 2123005, 2149025, 2123009, 2123403, 2149033, 2149011 Complication of hypertension drugs Drugs of the NHI Drug List Code starting with the following numbers: 2149110, 2149111, 2149112, 2149113, 2149114, 2149115, 2149116, 2149117, 2149118, 2149119, 2149120, 2149121, 2149122 Other Drugs of the NHI Drug List Code starting with the following numbers: 2149047, 2142004, 2149001, 2149017, 2145
Dyslipidaemia drugs	Statins Drugs of the NHI Drug List Code starting with the following numbers: 2189010, 2189011, 2189012, 2189013, 2189015, 2189016, 2189017, 2190101, 2190102, 2190103, 2190104 Fibrates Drugs of the NHI Drug List Code starting with the following numbers: 2183001, 2183002, 2183003, 2183004, 2183005, 2183006 EPA/DHA Drugs of the NHI Drug List Code starting with the following numbers: 2189019, 3399004 Other Drugs of the NHI Drug List Code starting with the following numbers: Dugs, other than the above, of the NHI Drug List Code starting with 218, 2900002, or 3133001.
Concomitant medication (other)	Drugs other than the above (diabetic drugs, hypertension drugs, or dyslipidaemia drugs).
Protease Inhibitor	Use the results of the drug name in the survey sheet (electronic) coded with the NHI Drug List (Appendix 1. List of Protease Inhibitors).
Renal excretory drugs	Use the results of the drug name in the survey sheet (electronic) coded with the NHI Drug List (Appendix 2. List of Renal Excretory Drugs).
Nesina treatment period (days)	Actual treatment period from the start date to the end date of Nesina treatment. However, the washout period is excluded from the treatment period. Calculate using the following formula: End of Nesina treatment – start date of Nesina treatment + 1 (grand total). (Consider the washout period.)
Mean daily dose of Nesina	Calculate using the following formula: Total of “daily dose of Nesina × Nesina treatment period at the relevant dose” / Nesina treatment period. For the calculation of Nesina treatment period, refer to the above. If the daily dose of Nesina is a number outside specification in the survey sheet (electronic) and is actual number, use the relevant number.

Term	Definition
HbA1c (NGSP value)	
The NGSP value only will be used in this analysis.
 
For the HbA1c (JDS value), calculate using the following formula: $\text{NGSP value (\%)} = 1.02 \times \text{JDS value (\%)} + 0.25\%$ 
 
The HbA1c (international standard value) will be handled as the NGSP value.

Change in HbA1c	
For HbA1c converted to the NGSP value, calculate using the following formula: Laboratory value at each testing time point – Laboratory value at the start of Nesina treatment.

Glycemic control achievement rate	
Divide the following two categories for the Glycemic control achievement rate:
 
HbA1c (NGSP converted value) [Unit %] NGSP (%): < 6.0, ≥6.0 / < 7.0, ≥ 7.0

non-HDL cholesterol	
Calculate using the following formula: “Total cholesterol” – “HDL cholesterol.”

Summary statistics	
Number of patients, mean, standard deviation, minimum, first quartile, median, third quartile, and maximum.

